2 PROTOCOL SYNOPSIS

Title A Phase 2, Randomized, Double-blind, Placebo-controlled, 6-Week, Parallel-design Study of the Efficacy and Safety of VX-150 in Treating Subjects With Pain Caused

by Small Fiber Neuropathy

Brief Title A Study to Evaluate the Efficacy and Safety of VX-150 in Treating Subjects With

Pain Caused by Small Fiber Neuropathy

Clinical Phase and Clinical Study Type

Phase 2 efficacy and safety

Objectives

Primary Objective:

To evaluate the efficacy of VX-150 for the treatment of pain caused by small fiber neuropathy

Secondary Objectives:

- To evaluate the safety and tolerability of VX-150
- To evaluate the pharmacokinetics (PK) of VRT-1207355 and the metabolite VRT-1268114

Endpoints Primary Endpoint:

Change from baseline in the weekly average of daily pain intensity on the 11-point numeric rating scale (NRS), as reported in the daily diary, at Week 6

Secondary Endpoints:

- Proportion of subjects with ≥30% reduction in the weekly average of daily pain intensity on the 11-point NRS, as reported in the daily diary, at Week 6
- Proportion of subjects with ≥50% reduction in the weekly average of daily pain intensity on the 11-point NRS, as reported in the daily diary, at Week 6
- Change from baseline in the Daily Sleep Interference Scale (DSIS) at Week 6
- Proportion of subjects categorized as improved at Week 6 on the patient global impression of change (PGIC) assessment
- Change from baseline in pain intensity on the 11-point NRS, as reported at study visits, at Week 6
- Plasma PK parameters of VRT-1207355 and the metabolite VRT-1268114
- Safety and tolerability based on the Columbia Suicide Severity Rating Scale (C-SSRS), incidence and type of adverse events (AEs), changes from baseline in clinically significant laboratory test results, vital signs, and ECGs at each visit

Number of Subjects Up to approximately 114 subjects

Study Population Males and females between the ages of 18 and 80 years, inclusive

Investigational Drug Active substance: VX-150

Activity: Na_v 1.8 blocker

Strength and route of administration: 1250 mg total dose daily, administered as

250-mg capsules orally

Study Duration

From Day -7 to last day of Safety Follow-up Visit, each subject will participate in the study for approximately 11 weeks.

Study Design

This is a Phase 2, randomized, double-blind, placebo-controlled, parallel-group, multicenter study. Up to approximately 114 subjects with small fiber neuropathy will be randomized 1:1 to VX-150 or placebo. Randomization will be stratified by sex and diagnosis of diabetes. Subjects with diabetes will not exceed approximately 60% of the total number of subjects. Subjects with diabetes and HbA1c \geq 8% and <11% at screening will not exceed approximately 20% of the total number of subjects.

This study will include:

- A 7-day Run-in Period to establish the baseline NRS pain score
- A 6-week Treatment Period
- A 28-day Safety Follow-up Period

Assessments Efficacy: NRS, DSIS, PGIC,

Safety: AEs, C-SSRS, clinical laboratory assessments, clinical evaluation of vital signs, ECGs, and physical examinations (PEs).

PK: Plasma PK parameters of VRT-1207355 and VRT-1268114

Statistical Analyses

The primary efficacy endpoint is the change from baseline in the weekly average of daily pain intensity on the 11-point NRS, as reported in the daily diary, at Week 6.

The primary analysis of the primary endpoint will be a within-group treatment comparison in the VX-150 treatment group. The analysis will be conducted using a mixed-effects model for repeated measures (MMRM). The between-group treatment comparison will also be generated using the same MMRM.

The model will include the change from study baseline in the weekly average of daily NRS pain score as the dependent variable; treatment, sex, diagnosis of diabetes, week, and treatment-by-week interaction as fixed effects; subject as a random effect; and baseline pain intensity score as a covariate. In the model, week will be treated as a class variable, and an unstructured covariance matrix will be assumed to model the within-subject variability.

The estimated mean and corresponding 95% CI for VX-150 will be provided for the within-group change. The CI will first be used to facilitate the comparison with 0; this will be followed by a comparison with 0.8. In addition, the estimated mean and corresponding 95% CI for the between-group difference will be provided.

3 SCHEDULE OF ASSESSMENTS

Schedules of Assessments are shown in Table 3-1 and Table 3-2.

Table 3-1 Study VX16-150-102: Screening

Event/Assessment	Screening ^a Day -28 to Day -1
Outpatient visit	X
Informed consent form (ICF)	X
Inclusion/exclusion criteria	X
Demographics	X
Medical history	X
History of drug and alcohol use	X
Weight, height, and body mass index (BMI) ^b	X
Vital signs ^c	X
Physical examination	X
Standard 12-lead electrocardiogram (ECG) ^d	X
Serum β-hCG (all female subjects)	X
Serum follicle-stimulating hormone (FSH) ^e	X
Serology (HBsAg, HCV, and HIV 1/HIV 2)	X
Serum chemistry ^f	X
Hematology ^f	X
Coagulation ^f	X
HbA1c ^g	X
Thyroid function test	X
Methylmalonic acid	X
Vitamin B12	X
Urinalysis	X
Drug and alcohol testing	X
Skin biopsy	X
Nerve conduction studies (NCS)	X
Education on appropriate expectations for being in a clinical study and reporting pain	X
11-pt numeric rating scale (NRS) pain score via daily diary from Days -7 through -1 h	X

Subjects must discontinue all treatment for neuropathic pain (including medications, supplements, and non-pharmaceutical therapies) by Day -14 (see Section 9.4.1).

b Weight and height will be measured with shoes off.

e Serum FSH is required for suspected postmenopausal female subjects only.

HbA1c will only be assessed for subjects with diabetes.

Vital signs (pulse rate, respiratory rate, blood pressure, and temperature) will be collected after the subject has been seated or supine for at least 5 minutes and before any 12-lead ECG assessment or blood sampling.

¹²⁻lead ECGs will be performed after subjects have been supine for at least 5 minutes. 12-lead ECGs will be done after vital signs and before any procedures that may affect heart rate (e.g., blood sampling).

f Blood samples will be collected for clinical laboratory assessments following a fast of at least 4 hours.

Subjects will report their average daily pain during the last 24 hours on the NRS.

Table 3-1 Study VX16-150-102: Screening

Event/Assessment	Screening ^a Day -28 to Day -1
Prior medications taken for the treatment of neuropathic pain ⁱ	X
Prior and concomitant medications ^j	Continuous from signing of ICF through Safety Follow-up Visit
Treatments and procedures	Continuous from signing of ICF through Safety Follow-up Visit
Adverse events	Continuous from signing of ICF through Safety Follow-up Visit

All medications previously taken for the treatment of neuropathic pain will be recorded. Subjects will also indicate whether the medications were discontinued, and if so, the reason for discontinuation.

All medications taken within 28 days before screening through the Safety Follow-up Visit will be recorded.

Table 3-2 Study VX16-150-102: Run-in Period, Treatment Period, and Safety Follow-up Visit

Event/Assessment	Day -7 (During Screening)	Day 1	Day 7 (± 1 Day)	Week 3 (± 3 Days)	Week 6 (± 3 Days)	ETT Visit ^a	Safety Follow-up Visit 28 (± 7) Days After the Last Dose of Study Drug
Clinic visit	X	X	X	X	X	X	X
Randomization		X					
Study drug dosing ^b			Day 1 thro	ough Week 6			
Weight ^c	X	X			X	X	X
Vital signs ^d	X	X	X	X	X	X	X
Standard 12-lead ECG ^e	X	X	X			X	X
Physical examination f		X					
Neurological examination			X	X	X	X	X
Urinalysis		X				X	X
Drug and alcohol testing	X			X	X	X	
Pregnancy test ^g	serum	urine	urine	urine	serum	serum	serum
Coagulation					X	X	X
Hematology		X		X	X		X
Serum chemistry		X		X	X		X
PK sampling ^h			X	X	X	X	

^a If the subject prematurely discontinues study treatment, an Early Termination of Treatment (ETT) Visit should be scheduled as soon as possible after the subject decides to terminate study treatment. Subjects who prematurely discontinue treatment will also be required to complete the Safety Follow-up Visit, approximately 28 (± 7) days after their last dose of study drug. If the ETT Visit occurs 3 weeks or later following the last dose of study drug, then the ETT Visit will replace the Safety Follow-up Visit, and a separate Safety Follow-up Visit will not be required.

b Study drug (VX-150 or placebo) will be administered daily under fasted conditions. The Day 7 dose will be administered at the clinic.

Pregnancy tests will only be performed for female subjects of childbearing potential.

c Weight will be measured with shoes off.

d Vital signs will be collected after the subject has been at rest (seated or supine) for at least 5 minutes.

Standard 12-lead ECGs will be performed after subjects have been supine for at least 5 minutes. 12-lead ECGs will be done after vital signs and before any procedures that may affect heart rate (e.g., blood sampling).

The neurological component of the Day 1 complete physical examination includes sensory testing conducted with the bedside sensory testing kit (BSTK). Symptom-directed physical examinations will occur at any time during the study if triggered by AEs or if deemed necessary by the investigator.

With the exception of Day 7, PK samples will be collected at any time during the study visit. On Day 7, 2 PK samples will be collected: 1 sample before the dose of study drug, and 1 sample 1 to 4 hours after the dose of study drug.

Table 3-2 Study VX16-150-102: Run-in Period, Treatment Period, and Safety Follow-up Visit

Event/Assessment	Day -7 (During Screening)	Day 1	Day 7 (± 1 Day)	Week 3 (± 3 Days)	Week 6 (± 3 Days)	ETT Visit ^a	Safety Follow-up Visit 28 (± 7) Days After the Last Dose of Study Drug
11-pt numeric rating scale (NRS) pain score via daily diary ⁱ		Day -7 through	n Week 6 or ETT Vi	sit via daily diary			
11-pt NRS pain score at study visits ^j	X	X	X	X	X	X	X
Daily Sleep Interference Scale (DSIS) ^k		Day -7 through	n Week 6 or ETT Vi	sit via daily diary			
Patient global impression of change (PGIC)		X	X	X	X	X	X
Columbia Suicide Severity Rating Scale (C-SSRS)		X	X	X	X	X	X
Study drug count			X	X	X	X	
Medications review		Cont	inuous from signing	of the ICF through	the Safety Follow-up	Visit	·····
Concomitant treatments and procedures		Cont	inuous from signing	of the ICF through	the Safety Follow-up	Visit	
Adverse events		Cont	inuous from signing	of the ICF through	the Safety Follow-up	Visit	

From Day -7 through Week 6 or ETT Visit, subjects will report their average daily pain during the last 24 hours on the NRS each evening. Subjects will also report their current pain immediately before each administration of rescue medication.

At study visits, subjects will report their average pain during the last 24 hours on the NRS.

From Day -7 through Week 6 or ETT Visit, subjects will report each morning on the previous night's sleep using the DSIS.

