9.1.3 Treatment Period

Treatment Period assessments are listed in Table 3-2.

All study periods will be conducted as described previously in Section 9.1. Dosing details are given in Section 9.3.2. During the Treatment Period, subjects will follow the pain treatment restrictions outlined in Section 9.4.1. Subjects will be permitted to take acetaminophen prn, following the guidelines in Section 9.4.1, as a rescue medication for intermittent pain.

Subjects who prematurely discontinue study drug treatment will remain in the study from the time of discontinuation of study drug treatment through the last scheduled study visit, and complete assessments for all study visits, as described in Section 9.1.5.

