9.1.5 Early Termination of Treatment

If the subject prematurely discontinues study drug treatment, an Early Termination of Treatment (ETT) Visit should be scheduled as soon as possible after the subject decides to terminate study drug treatment.

Subjects who prematurely discontinue treatment will also be required to complete the Safety Follow-up Visit, approximately 28 days (± 7) days after their last dose of study drug. The assessments performed at the Safety Follow-up Visit are listed in Table 3-2. If the ETT Visit occurs 3 weeks or later following the last dose of study drug, then the ETT Visit will replace the Safety Follow-up Visit, and a separate Safety Follow-up Visit will not be required.

If the subject withdraws consent for the study, no further evaluations should be performed, and no additional data should be collected. Vertex Pharmaceuticals Incorporated may retain and continue to use any data collected before such withdrawal of consent.

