11.6.2 Clinical Laboratory Assessments

At the Screening Visit, blood specimens will be collected for safety laboratory tests following at least a 4-hour fast. At other time points, fasting is only required with respect to dosing (see Section 9.4.2 and Section 9.5). On Day 1, blood samples will be collected before the first dose of study drug. At all other scheduled visits, these samples will be collected at any time during the clinic visit.

Blood and urine samples for clinical laboratory assessments will be collected as shown in Table 3-1 and Table 3-2. Laboratory test results that are abnormal and considered clinically significant will be reported as AEs (see Section 13.1).

The safety laboratory test panels are shown in Table 11-1.

Table 11-1 Safety Laboratory Test Panels

Serum Chemistry	Hematology	Urinalysis ^a
Glucose	Hemoglobin	Leukocyte esterase
Blood urea nitrogen ^b	Erythrocytes	Nitrite
Creatinine	Mean corpuscular volume	Urine protein
Sodium	Platelets	рН
Potassium	Leukocytes	Urine blood
Calcium	Differential (absolute and percent):	Specific gravity
Chloride	Eosinophils	Urine glucose
Magnesium	Basophils	
Bicarbonate	Neutrophils	
Phosphate	Lymphocytes	
Bilirubin, direct bilirubin	Monocytes	_
Alkaline phosphatase	Coagulation	
Aspartate transaminase (=SGOT)	Activated partial thromboplastin time	-
Alanine transaminase (=SGPT)	Prothrombin time	
Gamma-glutamyl transferase	Prothrombin time International	
Protein	Normalized Ratio	
Albumin		
Creatine kinase		
Thyrotropin		
Cholesterol		
Triglycerides		
Low-density lipoprotein-direct		
High-density lipoprotein		

Note: Screening Visit blood draws will be done after a minimum 4-hour fast.

^a If urinalysis results are positive for leukocyte esterase, nitrite, protein, or blood, microscopic examination of urine will be performed and results provided for leukocytes, erythrocytes, crystals, bacteria, and casts.

b If blood urea nitrogen cannot be collected, urea may be substituted.

Additional tests at screening: The following additional tests will be performed during screening to assess eligibility:

- Serum beta-human chorionic gonadotropin (β -hCG) for all female subjects
- Serum follicle-stimulating hormone (FSH) for suspected postmenopausal female subjects only. Levels will be within the laboratory's range for postmenopausal levels for subjects to be considered of non-childbearing potential.

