- Serology includes testing for hepatitis B surface antigen (HBsAg) and antibodies to hepatitis C virus (HCV) and human immunodeficiency viruses 1 and 2 (HIV 1/HIV 2).
- HbA1c (for subjects with diabetes only)
- Thyroid function test
- Methylmalonic acid
- Vitamin B12

Clinical laboratory assessments from screening will have no clinically significant findings that preclude participation in the study, as judged by the investigator, for a subject to receive study drug on Day 1.

Pregnancy testing for female subjects of childbearing potential (as defined in Section 11.6.6.1):

Pregnancy test results must be negative for female subjects of childbearing potential to receive study drug.

During treatment, if a urine or serum pregnancy test is positive, all study drug dosing will stop and the pregnancy will be confirmed with a serum β -hCG test. If confirmed, the pregnancy will be reported and the subject will be permanently withdrawn from study drug dosing as discussed in Section 11.6.6.2. If a pregnancy test is positive, the procedures outlined in Section 11.6.6.2 will be followed.

Drug and alcohol testing: Opiates, methadone, amphetamines/methamphetamines, cannabinoids, cocaine, barbiturates, and benzodiazepines will be assessed by a urine test. Alcohol will be assessed by a blood, urine, or breath test. Subjects may undergo random drug and alcohol testing if deemed appropriate by the investigator. Drug and alcohol test results must be negative for all subjects to receive study drug.

Additional Evaluations: Additional clinical laboratory evaluations will be performed at other times if judged to be clinically appropriate.

For purposes of study conduct, only laboratory tests done in the central laboratory may be used. Local laboratories may be used at the discretion of the local investigator for management of urgent medical issues. If a local laboratory test value is found to be abnormal and clinically significant, it will be verified by the central laboratory as soon as possible after the investigator becomes aware of the abnormal result. If it is not possible to send a timely specimen to the central laboratory (e.g., the subject was hospitalized elsewhere), the investigator may base the assessment of an AE on the local laboratory value.

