9 STATISTICAL ANALYSIS

9.1 General Considerations

The Schedule of Assessments is provided in Section 3 of CSP. The precision standards for reporting safety and efficacy variables are provided in an internal Biometrics document that specifies the programming rules including the precision for derived variables.

All individual subject data, including those derived, for subjects who were randomized or received at least 1 dose of study drug, i.e. All Subjects Set, will be presented in individual subject data listings as described.

Continuous variables will be summarized using the following descriptive summary statistics: the number of subjects (n), mean, standard deviation (SD), standard error (SE), median, minimum value (min), and maximum value (max).

Categorical variables will be summarized using counts and percentages.

Baseline value for the NRS via daily diary and the DSIS will be defined as the average score of at least 4 nonmissing scores from Day -7 to Day -1. For all other variables baseline will be defined as the most recent nonmissing measurement collected before the initial administration of study drug unless specified otherwise.

Change (absolute change) from baseline will be calculated as post-baseline value – baseline value unless otherwise specified.

Treatment-emergent (TE) Period will be defined as the time from dosing with study drug until the following time point:

- For enrolled subjects who have a Safety Follow-up Visit: through the Safety Follow-up Visit
- For enrolled subjects who do not have a Safety Follow-up Visit, the earliest of
 - 35 days after the last dose of study drug, or
 - the ETT Visit if that visit is 3 weeks or later following the last dose of study drug (see Section 9.1.5 of CSP)

Unscheduled visits: Unscheduled visit measurements will be included in analysis as follows:

- In scheduled visit windows per specified visit windowing rules.
- In the derivation of baseline/last on-treatment measurements.
- In the derivation of maximum/minimum on-treatment values and maximum/minimum change from baseline values for safety analyses.
- In individual subject data listings as appropriate.

Visit windowing rules: The analysis visit windows for protocol-defined visits are provided in [Appendix A](#).

Incomplete/missing data will not be imputed, unless otherwise specified.

Outliers: No formal statistical analyses will be performed to detect or remedy the presence of statistical outliers, unless specified otherwise.

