12 LIST OF APPENDICES

Appendix A: Analysis Visit Windows for Safety and Efficacy Assessments

Table 12-1 Analysis Visit Windows for Safety and Efficacy Assessments

Assessment	Visit ¹	Target Study Day per the protocol	Analysis Visit Window (in study days)
Safety Assessment			
Hematology	Baseline	1	[Screening visit, Pre-dose Day 1]
Serum Chemistry	Week 3	22	[1*, 32]
	Week 6	43	[33, 57]
	Safety Follow-up Visit	N/A	Nominal
Coagulation	Baseline	N/A	[Screening visit, Pre-dose Day 1]
	Week 6	43	[1*, 57]
	Safety Follow-up Visit	N/A	Nominal
Standard 12-Lead ECG	Baseline	1	[Screening visit, Pre-dose Day 1]
	Day 7	7	[1*, 57]
	Safety Follow-up Visit	N/A	Nominal
Vital Sign	Baseline	1	1
	Day 7	7	[2, 14]
	Week 3	22	[15, 32]
	Week 6	43	[33, 57]
	Safety Follow-up Visit	N/A	Nominal
C-SSRS	Baseline	1	[-1, 1]
	Day 7	7	[2, 14]
	Week 3	22	[15, 32]
	Week 6	43	[33, 57]
	Safety Follow-up Visit	N/A	Nominal

Table 12-1 Analysis Visit Windows for Safety and Efficacy Assessments

Assessment	Visit ¹	Target Study Day per the protocol	Analysis Visit Window (in study days)
Efficacy Assessment			
NRS via daily diary	Baseline	N/A	[-7, -1] ²
DSIS via daily diary	Week 1	N/A	[1*, 7]
	Week 2	N/A	[8, 14]
	Week 3	N/A	[15, 21]
	Week 4	N/A	[22, 28]
	Week 5	N/A	[29, 35]
	Week 6	N/A	[36, 42]
NRS reported at study visits	Baseline	1	Before first dose of study drug
PGIC			
	Day 7	7	[1*, 14]
	Week 3	22	[15, 32]
	Week 6	43	[33, 57]
	Safety Follow-up Visit	N/A	Follow the individual visit window to be mapped to individual visits if measured before / on Day 57 or remain as SFU if otherwise.

1* only include day 1 post-dose measurements.

¹ Visit name for analysis purpose is used to report data in tables and figures.

²Only include 7 day measurements before the randomization day.

Notes:

The analysis visit windows will be applied using the following rules for both scheduled and unscheduled visits:

1. If no numerical measurement is available within a visit window, the measurement will be considered missing for the visit.
2. If there is more than 1 numerical measurement available within the same visit window, use the following rules:
 - a. a. For efficacy assessments: if there are multiple measurements within a visit window,
 - i. The measurement closest to the target day will be used; or
 - ii. If there are multiple measurements within the same distance from the target day, the latest measurement will be used.
 - b. For safety assessments: if there are multiple measurements within a visit window,

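### Hematology and serum chemistry are not scheduled at the ETT Visit, although a late ETT Visit replaces the Safety Follow-up Visit, where both are drawn

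*Protocol*

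**What the plan says.** In protocol Table 3-2, hematology and serum chemistry are marked at Day 1, Week 3, Week 6 and Safety Follow-up. The ETT cell is blank in both rows. Section 11.6.2 sets no separate timing and defers to the tables: "Blood and urine samples for clinical laboratory assessments will be collected as shown in Table 3-1 and Table 3-2". It adds a discretionary route: "Additional clinical laboratory evaluations will be performed at other times if judged to be clinically appropriate".

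Footnote a to Table 3-2 and Section 9.1.5 carry the same replacement rule. Its condition is a delay of at least 21 days between stopping drug and the stopping visit. Its consequence is stated as follows: "then the ETT Visit will replace the Safety Follow-up Visit, and a separate Safety Follow-up Visit will not be required". Neither place says which column of the table applies at the replacing visit.

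Section 9.1.3 keeps subjects who stop drug in the study and has them "complete assessments for all study visits, as described in Section 9.1.5". Section 9.1.5, however, names only the ETT Visit and the Safety Follow-up Visit.

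SAP Section 9.1 recognizes the late ETT Visit. For subjects without a Safety Follow-up Visit, the treatment-emergent period ends at the earlier of 35 days after the last dose and "the ETT Visit if that visit is 3 weeks or later following the last dose of study drug". SAP Appendix A gives hematology and chemistry a Week 3 window (post-dose Day 1 to Day 32), a Week 6 window (Days 33 to 57) and a nominal Safety Follow-up Visit. It has no rule for an ETT Visit that stands in for Safety Follow-up.

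**The concern.** Subjects who stop early include those in whom laboratory safety data matter most. Section 9.6 sends subjects with unacceptable toxicity to the ETT procedure, and Section 11.6.4 stops dosing for a QTcF above threshold. The unscheduled panels hold the transaminases, bilirubin, creatinine, potassium, magnesium and blood counts (Table 11-1), and SAP Appendix D sets thresholds on most of these. Results close to the time of stopping help in judging whether the drug caused a change. A transient abnormality may have resolved by a draw several weeks later.

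Discretionary testing covers the subject whose investigator already suspects a problem. It does not cover a silent change in someone who stops for another reason.

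The omission looks unintended. Coagulation, urinalysis, PK, ECG and the serum pregnancy test are all scheduled at ETT, and neither document gives a reason for leaving out these two panels.

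**Working it through.** There is no stated figure to reproduce. The check is a reading of the schedule followed by day arithmetic.

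**1. The cells.** Both rows fill all seven visit columns of Table 3-2, and the neighboring laboratory rows align with them.

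| Row | Day -7 | Day 1 | Day 7 | Week 3 | Week 6 | ETT | Safety Follow-up |
|---|---|---|---|---|---|---|---|
| Hematology | – | X | – | X | X | – | X |
| Serum chemistry | – | X | – | X | X | – | X |
| Coagulation | – | – | – | – | X | X | X |
| Urinalysis | – | X | – | – | – | X | X |

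**2. The row count.** Rows individually marked at Safety Follow-up are clinic visit, weight, vital signs, ECG, neurological examination, urinalysis, pregnancy test, coagulation, hematology, serum chemistry, visit NRS, PGIC and C-SSRS, which makes 13. Of these, 13 − 2 = 11 are also marked at ETT. The two exceptions are hematology and serum chemistry.

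**3. Prompt ETT, with only the Section 9.1.5 visits attended.** Safety Follow-up is 28 ± 7 days after the last dose, so the first scheduled panel after stopping comes 21 to 35 days after the last dose. Day 7 has no panel either. A subject who stops before Week 3 on this path has nothing scheduled between the Day 1 baseline and Safety Follow-up.

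**4. Replacing ETT.** The earliest replacing visit is on last dose day + 21.

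- The Week 6 visit window is Day 43 ± 3, or Days 40 to 46 (target day from SAP Appendix A, tolerance from Table 3-2).
- Last dose on Day 25: 25 + 21 = 46, still inside the window.
- Last dose on Day 26: 26 + 21 = 47, after the window. From Day 26 on, no scheduled visit with these panels can come after the replacing ETT.
- A subject who stops before Week 3, attends only the Section 9.1.5 visits and has a replacing ETT has no scheduled post-baseline panel at all.

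**5. SAP mapping, if a panel is drawn at a replacing ETT.** The Week 6 laboratory window ends on Day 57.

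- Last dose on Day 36: 36 + 21 = 57, inside the window.
- Last dose on Day 37: 37 + 21 = 58, outside it.

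From Day 37 on, a sample at a replacing ETT falls in no numeric window. It reaches the Safety Follow-up summary only if the visit is recorded under that name. Samples up to Day 57 already fall in the Week 3 or Week 6 window, because the Appendix A rules apply broadly: "The analysis visit windows will be applied using the following rules for both scheduled and unscheduled visits".

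**6. Number of subjects.** The documents do not say how many ETT Visits to expect. The only related figure is the sample-size allowance for withdrawal of up to 20%: 0.20 × 114 = 22.8, or about 23 subjects over both arms. This is a planning ceiling for withdrawal, not a count of ETT Visits, and the replacing-ETT group would be some unknown part of it.

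**The case against.** The strongest reply is that the protocol already keeps these subjects under observation. Section 9.1.3 has them complete all study visits, Section 9.7 says they continue to be followed, and Week 3 and Week 6 both draw the panels. Section 9.1.5 does not say that its two visits are the only ones. On this reading, a subject whose last dose is on Day 26 is still due at Week 6, which is 40 − 26 = 14 to 46 − 26 = 20 days after stopping. This stands as mitigation, and some subjects will have those results. But Sections 9.1.3 and 9.7 both point to Section 9.1.5, which names neither Week 3 nor Week 6, so sites may read the duty differently. Even the generous reading puts no panel at the stopping visit itself.

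The second reply is that a visit which replaces Safety Follow-up naturally takes over its tests. Section 9.1.5 refers to the Safety Follow-up assessments immediately before stating the rule. A site could reasonably read it so. The ETT column says otherwise, however, and Section 11.6.2 makes the table decisive, so the text is at best ambiguous.

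Third, the ETT Visit is to be held as soon as possible, so a 21-day delay should be uncommon. That stands. It limits the loss of the Safety Follow-up panels but not the gap at a prompt ETT.

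Fourth, the SAP gap is minor. That also stands. All safety data are listed by subject, and the threshold listing covers unscheduled time points (SAP Sections 9.4 and 9.4.2), so a late sample would be missing only from by-visit summaries. How the visit is named in the eCRF cannot be seen from these documents.

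Finally, the protocol introduction reports no safety concerns to date, and extra tests are allowed when clinically appropriate. Both lower the expected harm. Neither provides routine testing in subjects without symptoms.

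**Conclusion.** The concern holds. Followed as written, the schedule omits hematology and serum chemistry at every ETT Visit. When that visit replaces Safety Follow-up, it omits them at the final visit as well.

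For a prompt ETT, the first scheduled panels after stopping come 21 to 35 days after the last dose, assuming the subject attends only the visits that Section 9.1.5 names. With attendance at Week 3 or Week 6 the gap can be shorter. The more serious case, a replacing ETT, is probably rare and cannot be sized from the documents.

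This is a weakness in safety data collection and does not touch the primary or secondary efficacy analyses. It should be corrected because the gain is real and the cost is small. The conclusion rests on the two ETT cells being truly blank. A mark lost in the copy of the table cannot be ruled out entirely, but the full seven-column rows and the aligned neighbors make it unlikely.

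**What to change.** 1. In protocol Table 3-2, mark hematology and serum chemistry at the ETT Visit.
2. In footnote a and Section 9.1.5, add one sentence: an ETT Visit that replaces the Safety Follow-up Visit includes all Safety Follow-up assessments.
3. In SAP Appendix A, add one line mapping a replacing ETT Visit to the Safety Follow-up Visit. Other ETT samples up to Day 57 need no new rule.

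The cost is two table cells, one sentence in two places and one SAP line. For the subject it means a little more blood, assumed here to be at most two tubes (the documents give no volumes), at a visit that already draws coagulation and PK samples.
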